#### E. OVERVIEW OF SELECTION OF CASES AND CONTROLS

Vaccinated cases (SAB) and controls (deliveries) for this protocol will be selected in a 4-phase process (Figure 1), with a targeted final sample of 100 cases, with each case matched to at least 1 control in the final analysis. In phase 1, 140 potential cases will be initially identified in claims-based and administrative data. Also in phase 1, the initial step of identifying deliveries and estimating their pregnancy start will occur using claims-based and administrative data. If more than 140 potential cases are identified in electronic data, we will randomly sample 70 cases from each Data Partner. In phase 2, chart review will be conducted on potential cases to confirm SAB, date of SAB, and obtain pregnancy start date; potential cases will only be retained if vaccination occurred during the gestational period of interest (-4 weeks gestation to SAB event date). In phase 3, for each chart-confirmed case, we will identify 2 potential controls with the same age, pregnancy start, and vaccination between -6 weeks gestation and 2 weeks past the case's gestational age at SAB, based upon electronic data. We will randomly sample a minimum of 2 controls for each case. In the final phase, we will chart review potential controls to confirm pregnancy start, vaccination, and gestational age at vaccination.

Mini-Sentinel

Figure 1: Case and control selection for PRISM Influenza Vaccines and Pregnancy Outcomes Assessment

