#### K. CASE-TIME-CONTROL DESIGN

As proof-of-concept, a case-time-control study design will be implemented to examine whether risk of SAB is elevated in specific time periods following TIV or in specific gestational periods following TIV. We will identify SAB cases that were vaccinated between -4 weeks gestation until the date of the SAB. Since the likelihood of receiving TIV differs by gestational age and calendar time, we will match each case to a vaccinated control based on Data Partner, maternal age, and pregnancy start, where the control must have received TIV between -4 weeks gestation and the case's gestational age at SAB. In order to understand the feasibility of using the case-time-control design in Mini-Sentinel, we will first examine (1) the validity of claims data for identifying SAB; (2) the validity of birth certificate and claims data for identifying start among live delivery controls for matching them to chart-confirmed cases; and (3) the validity of using claims data for matching cases to controls on confounders, if matching on factors other than DP and pregnancy start is ultimately implemented. The details of the descriptive statistics for Primary Objectives 1-3, which will be used to address each of these aims, are described further in the analytic section of the protocol.

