**PRISM Surveillance Protocol** 

## IV. ANALYSIS

#### A. ANALYSIS FOR PRIMARY OBJECTIVES (OBJECTIVES 1-3)

In Primary Objective 1, we will determine the feasibility of using claims data to identify potential cases for the proposed study. We will examine the positive predictive value of claims codes for SAB, using chart review as the "gold standard". We will estimate the positive predictive value (i.e., chart confirmed SAB cases divided by all potential SAB cases identified via claims data) overall, by maternal age group (18-24, 25-29, 30-34, and 35-39 years), and by claims codes (i.e., specific ICD9 or CPT code).

In addition to validating case status in Primary Objective 1, we will estimate the proportion of cases that need to be discarded because vaccination occurs prior to the period of interest (i.e., prior to -4 weeks gestation). We will also identify the optimal look-back period for vaccine codes in relation to SAB codes in electronic data to minimize the number of cases that need to be discarded because vaccination occurred before -4 weeks gestation. To accomplish this, we will tabulate the proportion of excluded cases due to this reason by days between vaccine and SAB codes in electronic data.

In Primary Objective 2, we will examine the accuracy of gestational age data in claims and in birth certificate data for the purposes of identifying pregnancy start among live delivery controls, who will be matched to chart-confirmed cases. We will estimate the proportion of controls that must be discarded because their chart-confirmed pregnancy start date is not within the pre-specified number of days from the case date. We will estimate the proportion of controls that must be discarded because their vaccination is determined via chart review to occur after the case's gestational age at SAB. We will also examine whether the proportion of discarded controls due to each of these two reasons differs by whether birth certificates or claims data were used to estimate pregnancy start date in electronic data. Finally, we will describe the distribution of matched case-control pairs by difference in pregnancy start date in cases and controls. We will stratify by whether birth certificates or claims data were used to estimate gestational age.

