In Primary Objective 3, we will determine the accuracy of claims data for matching potential cases and controls on potential confounders. We will determine the positive predictive value in cases and controls for each of the confounders matched upon. We will also determine the proportion of matched case-control pairs that have concordant status in chart data for each matching factor (i.e., confounder).

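### As written, Objective 1's PPV falls with every chart that is not obtained, and Objective 3 may return no result because it validates only confounders used for matching

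*Protocol*

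**What the plan says.** **Objective 1.** Section IV.A takes chart review as the reference standard and defines PPV as "chart confirmed SAB cases divided by all potential SAB cases identified via claims data". It is to be reported overall, by claims code and by maternal age in the groups "18-24, 25-29, 30-34, and 35-39 years". Section III.D restricts the study population to ages 18 through 34.

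Section III.E sets the number of women going to review: "In phase 1, 140 potential cases will be initially identified in claims-based and administrative data". It adds: "If more than 140 potential cases are identified in electronic data, we will randomly sample 70 cases from each Data Partner". Section V.B allows, when discussing power, that fewer charts may be obtained than expected. No section says how a woman without a chart is treated in the PPV.

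**Objective 3.** Section II.A lists the accuracy of potential confounders in claims as a primary objective, with no condition beyond its purpose of supporting matching. The analysis in IV.A is narrower: "We will determine the positive predictive value in cases and controls for each of the confounders matched upon". It adds the proportion of matched pairs whose chart status agrees, again by matching factor. Section III.H makes matching on diabetes, obesity, asthma, multiparity, four types of infection and fever depend on having enough controls. Section III.K makes the validation itself conditional: "if matching on factors other than DP and pregnancy start is ultimately implemented". Section V.B, by contrast, says without condition that infections will be matched.

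**The concern.** A PPV against a chart standard is defined only for women who have a chart result. With all potential cases in the denominator, a missing chart has the same effect as a chart that refutes the diagnosis. The figure then mixes two different things: whether the code is right and whether the record could be retrieved. The age-specific and code-specific PPVs are affected in the same way, so a difference in retrieval between codes would look like a difference in validity.

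For Objective 3, the plan makes the existence of a result depend on a later decision about matching. Whether claims are accurate enough to match on is what a future study needs to know before it decides to match, so the dependence runs the wrong way.

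The protocol says its main purpose is to optimise claims and birth-certificate algorithms, and it treats the vaccine-risk estimates as pilot work. A sound code algorithm could look poor because of missing charts, and one of three primary objectives could go unanswered.

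**Working it through.** **Is there a figure to reproduce?** No. The protocol states no expected PPV, PPV precision or retrieval rate. The nearest figure is the target in III.E, "with a targeted final sample of 100 cases, with each case matched to at least 1 control in the final analysis", from 140 potential cases: 100/140 = 0.71. That is a yield, not a PPV. It also absorbs missing charts, missing last menstrual period, losses before 6 weeks, vaccination outside the window and failure to find a control.

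**Objective 1.** Let n be the potential cases selected, r the fraction of charts obtained and p the PPV among reviewed charts.

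- As written: confirmed / n = (n × r × p) / n = r × p.
- Among adjudicated charts: (n × r × p) / (n × r) = p.

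The two agree only at r = 1. Input from the protocol: n = 140. Assumed: p = 0.90, and r from 100% down to 60%. Counts are rounded to whole women. The best case counts every missing chart as confirmed.

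| Retrieval | Charts | Confirmed | As written | Among reviewed | Best case |
|---|---|---|---|---|---|
| 100% | 140 | 126 | 126/140 = 0.90 | 126/140 = 0.90 | 0.90 |
| 90% | 126 | 113 | 113/140 = 0.81 | 113/126 = 0.90 | (113+14)/140 = 0.91 |
| 80% | 112 | 101 | 101/140 = 0.72 | 101/112 = 0.90 | (101+28)/140 = 0.92 |
| 70% | 98 | 88 | 88/140 = 0.63 | 88/98 = 0.90 | (88+42)/140 = 0.93 |
| 60% | 84 | 76 | 76/140 = 0.54 | 76/84 = 0.90 | (76+56)/140 = 0.94 |

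At 80% retrieval the 95% Wilson intervals are 0.64 to 0.79 as written and 0.83 to 0.94 among reviewed charts, so they do not overlap. The written ratio is the worst-case bound, in which no missing chart would have confirmed. It is useful as a bound and wrong as the estimate.

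The same arithmetic applies by stratum. Two codes that both have p = 0.90, one with 90% and one with 60% retrieval, would be reported as 0.81 and 0.54.

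**Age strata.** The fourth group starts at 35 and eligibility stops at 34, so the row is empty by design.

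**Objective 3.** The statements side by side:

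1. II.A: accuracy of claims confounders is a primary objective.
2. IV.A: PPV and pair concordance only for factors matched upon.
3. III.H: matching on the nine coded factors (diabetes, obesity, asthma, multiparity, urinary, respiratory, gastrointestinal and sexually transmitted infections, fever) only if controls suffice.
4. III.K: validation only if such matching is implemented.
5. V.B: infections will be matched, which conflicts with item 3.

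If no extra matching is done, zero of the nine coded confounders receive a PPV. Yet III.O abstracts asthma, diabetes, obesity, febrile illness, medically attended infections and gravidity from the chart in any event, mainly for description. Section III.I also limits cases left without a control to Objectives 1 and 2, so their charts are lost to Objective 3 although they have been read.

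**The case against.** The strongest reply on Objective 1 is that a PPV against chart review presupposes a chart. Sections III.G and III.O read as though every potential case is reviewed, nothing labels an unread chart a false positive, and the remark about fewer charts in V.B concerns power. This shows that the intention may be sound. It does not change the formula, which the protocol fixes itself and which has no exception for missing charts.

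A reader might infer more than the text supports:

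- *That women never sampled for review also enter the denominator.* If all 140 sampled charts were read and 126 confirmed, an assumed pool of 300 would give 126/300 = 0.42. But III.E also calls the 140 selected women potential cases, so this needs the least plausible reading.
- *That false negatives are ignored altogether.* The pair concordance in IV.A would reveal some of them among pairs matched on absence of a condition. It is limited to matched factors, so it does not rescue an unmatched confounder.
- *That confirmed losses later excluded would drop from the numerator.* Section III.O defines confirmation as an intrauterine pregnancy with natural loss before 20 weeks, separately from the exclusions for vaccination timing and early loss.
- *That the overall PPV must be weighted by Data Partner sampling fractions.* This presumes a pooled-population target that the protocol does not state.

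On Objective 3, the reply is that its scope is deliberate: it serves matching, and III.K states the condition openly. That stands as a description of the plan, but a primary objective that may have nothing to report is still badly fixed when most of the chart data will be available. The reply also rightly warns against sensitivity and specificity among controls chosen on their claims status, because the matching fixes how common that status is.

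**Conclusion.** The point holds for two stated rules and one stratum.

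Objective 1 reports retrieval times PPV instead of PPV. The size depends on a retrieval rate the protocol does not give. At an assumed 0.90 among reviewed charts, the understatement is about 0.09 at 90% retrieval, 0.18 at 80% and 0.36 at 60%, and nil at full retrieval. Taking 0.90 as the right answer also assumes that charts not obtained resemble those obtained, which is why bounds are needed.

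Objective 3 can end with no result for any coded confounder, and the statements on infection matching in III.H and V.B contradict each other. The 35-39 stratum contradicts the eligibility range. It is harmless in itself but should be corrected.

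The documents do not support a claim that unsampled women are counted as failures or that PPV is the only accuracy measure planned.

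**What to change.** **Objective 1 (IV.A).** Define PPV overall, by age and by code as confirmed SABs divided by potential cases with a chart obtained and adjudicated. Report the number and proportion of charts not obtained separately, by the same strata, with a worst-case bound (none confirmed) and a best-case bound (all confirmed). Remove the 35-39 group.

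**Objective 3 (IV.A, III.K).** Report claims-versus-chart PPV, and negative predictive value where the chart allows it, for every claims-coded confounder that is also abstracted. Do this in all reviewed cases and controls, whether or not the factor was matched upon, and include cases left unmatched under III.I. Keep pair concordance for factors actually matched. Note that measures in controls selected on claims confounder status reflect that selection. Reconcile III.H and V.B on infection matching.

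**Cost.** Changes of wording and a few extra tables, mostly from data the plan already collects. Parity may need to be added to the abstraction form, because III.O lists only gravidity while III.H matches on multiparity.

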# F. IDENTIFYING POTENTIAL CASES AND CONTROLS IN CLAIMS-BASED AND ADMINISTRATIVE DATA (PHASE 1)

#### 1. Cases

The inclusion criteria for cases and controls are summarized in Appendix 1. Using claims and administrative data, women who have experienced a SAB will be initially identified using the codes in Appendix 2 occurring in the inpatient, emergency department, or ambulatory care setting. To avoid including follow-up visits, a 98-day (i.e., 14 week) washout period will be used to identify incident SAB events. If there are multiple incident SAB events for a given patient, we will select the first chronological event in the study period. Though the average gestational length of pregnancies ending in miscarriage is shorter (i.e., 10 weeks), we chose the 14-week washout period to enhance the specificity for detecting incident SAB events. Initially, inclusion based on period of enrollment will be conducted through the use of administrative and claims-based data; women whose pregnancies have ended in a SAB will only be considered a potential case if based on claims-based and administrative data, they are enrolled continuously for the 244 days prior to their medical encounter for SAB. The 244-day pre-SAB enrollment criterion for potential cases incorporates a 90-day period prior to pregnancy start, 140-day period for the maximum gestational length for a pregnancy ending in SAB, and a 14-day period to allow for delays in seeking medical attention for SAB.

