We will also initially require, based on electronic data, potential cases to have received TIV within the 1-182 days prior to the SAB code. This 182-day (i.e., 26 week) period was selected to enhance our ability to detect vaccinations during the gestational period of interest (-4 weeks gestation through SAB event date) and incorporates a 20-week period corresponding to the latest gestational age at which a SAB may occur, a 4-week period corresponding to the pre-gestational period of interest, and a 2-week period to allow for delays in seeking medical care for miscarriage. After the SAB event date is confirmed, we will ensure that cases are enrolled for a minimum of 90 days prior to pregnancy start through the SAB event date and will only retain cases with TIV in the period of interest (-4 weeks gestation through SAB event date). While we will use claims data to initially identify potential cases, we will limit our analysis to chartconfirmed cases and will use medical record data to identify the start of pregnancy and the date of SAB to reduce misclassification of timing of exposure with respect to gestational age and days in relation to SAB. The process of medical record review will be described later in the protocol.

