#### **B. LIMITATIONS**

Foremost, we will have limited power to detect small or modest effect sizes in this feasibility study. For example, our target sample size of 100 cases and 100 controls corresponds to approximately 80% power to detect a relative risk of 2.4 or above for the pilot objective of examining whether there is an elevated risk with exposure during the risk interval of 2-6 weeks gestation. Of note, this power calculation may be somewhat optimistic if we obtain fewer charts than originally anticipated or if a significant portion of cases or controls do not meet study inclusion criteria (e.g., not vaccinated during the period of interest), or depending on the distribution of cases and controls in 3 different gestational age risk periods. Our power calculation may also be an overestimate if our assumptions used to calculate power, such as the gestational age distribution of SAB or the gestational distribution of vaccination among controls (both of which are based on published literature), are incorrect. However, the primary objectives of this proof-of-concept protocol are to determine optimal algorithms for using claims and birth certificate data for pregnancy related studies. As such, this study will have the capability to inform future studies on pregnancy outcomes in the Mini-Sentinel.

The current study's case definition is limited to women seeking medical care for SAB. A large percentage of miscarriages occur without medical care, particularly in those occurring early during pregnancy. A significant proportion of these early pregnancies, particularly in the first six weeks, are unrecognized by the mother, making detection difficult. Thus, results may not be applicable to the effects of vaccines on

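### The criterion for the optimal vaccine look-back counts only discarded cases, so it favours short windows that lose eligible vaccinations before and around conception

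*Protocol*

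**What the plan says.** Protocol IV.A, under Primary Objective 1, plans to "identify the optimal look-back period for vaccine codes in relation to SAB codes in electronic data to minimize the number of cases" lost because vaccination preceded -4 weeks' gestation. The method is a table of the proportion of cases excluded for that reason, by days between the vaccine code and the SAB code. No second criterion is named.

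The window used in this study is set in III.F.1, which requires "potential cases to have received TIV within the 1-182 days prior to the SAB code". The reason given is detection: "This 182-day (i.e., 26 week) period was selected to enhance our ability to detect vaccinations during the gestational period of interest". The window "incorporates a 20-week period corresponding to the latest gestational age at which a SAB may occur", to which 4 weeks before pregnancy and 2 weeks for delay in seeking care are added.

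Three other statements bear on the point. III.F.1 puts the average length of a pregnancy ending in miscarriage at 10 weeks. III.O excludes SABs before 6 weeks. III.K (Pilot Objective 5) names -4 through 4 weeks as one of three gestational risk intervals.

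**The concern.** A look-back has two kinds of error. If it is too long, charts are pulled for women vaccinated before the period of interest. If it is too short, women who were vaccinated within that period are never selected. The stated criterion counts only the first kind. The second falls mainly on the earliest eligible vaccinations, those before and around conception, because they lie furthest from the SAB.

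Section II gives the overarching goal as optimising algorithms for pregnancy studies, and V.B says the results will inform later Mini-Sentinel work. The look-back is therefore one of the study's products. Chosen by the stated criterion, it could pass to later studies a window that removes much of the exposure needed to examine the -4 to 4 week interval.

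**Working it through.** **The plan's own figure.** (20 + 4 + 2) weeks x 7 = 182 days. This reproduces.

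**Longest look-back with no timing discards.** The earliest SAB kept is at 6 weeks and the earliest eligible vaccination is at -4 weeks. The shortest eligible period is therefore (6 + 4) x 7 = 70 days, and a vaccination 70 days or less before any retained SAB is at or after -4 weeks. A delay between the SAB and its code does not break this bound, because the lag from vaccine to code is then the longer of the two. The bound assumes that SABs before 6 weeks are removed before timing discards are counted, and that the code does not precede the SAB date.

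**Direction.** Windows are nested: every case selected with a shorter look-back is also selected with a longer one. The number of timing discards is zero up to 70 days and can only stay level or rise after that.

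**What a 70-day look-back misses.** For an SAB at g weeks (6 or later), the eligible days are 7(g + 4) and the days missed are 7(g + 4) - 70 = 7(g - 6).

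| SAB at | Eligible days | Missed at 70 days | Share | Gestational weeks missed |
|---|---|---|---|---|
| 6 weeks | 70 | 0 | 0% | none |
| 8 weeks | 84 | 14 | 17% | -4 to -2 |
| 10 weeks | 98 | 28 | 29% | -4 to 0 |
| 12 weeks | 112 | 42 | 38% | -4 to 2 |

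These are shares of eligible days. They need no assumption about when women are vaccinated.

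**Illustration in cases.** Turning days into cases needs assumptions the protocol does not give. Here gestational age at SAB is spread over 6 to 20 weeks with mean 10 (a scaled beta distribution, shapes 1.6 and 4.0), vaccination is even over the 182 days, and the code falls on the SAB date.

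| Look-back (days) | Selected cases discarded for timing | Eligible cases retained | Retained among those vaccinated at -4 to 4 weeks |
|---|---|---|---|
| 70 | 0% | 71% | 51% |
| 98 | 7% | 93% | 87.5% |
| 112 | 15% | 97% | 95% |
| 140 | 30% | 99.9% | 99.8% |
| 182 | 46% | 100% | 100% |

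Judged by discards alone, 70 days looks best in this table. With the retention column beside it, 70 days is plainly poor. A 95% retention rule would land between 98 and 112 days. The percentages would change under other assumptions; the zero-discard bound at 70 days would not.

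**The case against.** Four points can be made for the plan.

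- The planned table reports proportions by lag. With the counts behind them, the complement shows the cases not excluded for timing, so a careful reader could see where eligible cases run out. This stands: the information will be in the data, since all cases are drawn under 182 days. But the stated aim does not use it.
- No automatic selection rule is given, and III.F.1 states a detection purpose. An analyst who kept that purpose in mind would not choose a very short window. This is fair as a prediction of conduct, but IV.A names only the one aim.
- A reader might infer that the criterion must pick a window that drops every vaccination before conception. It need not. All windows up to 70 days tie at zero, so the minimiser is not unique, and an SAB at 6 weeks loses nothing at 70 days.
- Case selection in this study is unaffected, because it uses 182 days.

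A stronger inference is also tempting: that the 182-day window makes the 140 charts fall well short of 100 cases and of 80% power. For a 10-week SAB, 98/182 x 140 = 75. The documents do not establish this. The figure needs vaccination timing to be even, whereas III.K and III.M say the likelihood of vaccination varies with gestational age and calendar time. If vaccination were r times as frequent from pregnancy start, the eligible share would be (4 + 10r)/(16 + 10r), which reaches 100/140 at r = 2.6. With mean gestational age at SAB of 9 to 11 weeks and vaccination 0.5 to 5 times as frequent from week 5, the yield runs from about 64 to 109 before other losses. Any power figure at a smaller size also needs a control exposure share that the protocol does not give. III.E describes 100 as a target: "with a targeted final sample of 100 cases, with each case matched to at least 1 control in the final analysis". V.B makes the power conditional on it: "our target sample size of 100 cases and 100 controls corresponds to approximately 80% power to detect a relative risk of 2.4". V.B then names vaccination outside the period of interest as a reason the power may be optimistic.

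**Conclusion.** The point holds for the look-back criterion. As written, it is one-sided: zero discards at every window up to 70 days, never fewer as the window lengthens, and no weight on eligible cases lost. At 70 days, an SAB at the protocol's average of 10 weeks loses 28 of 98 eligible days (29%), all of them before pregnancy start. This rests on the 6-week exclusion, the -4 week limit and the two counting assumptions given with the bound. It conflicts with the stated purpose of the 182-day window and with the -4 to 4 week risk interval.

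The consequence is for an output of Primary Objective 1 and its later use. No shortfall in the number of cases or in power is claimed.

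**What to change.** In IV.A, replace the single aim with a two-sided one. For each candidate look-back, tabulate (a) the share of selected cases discarded because vaccination preceded -4 weeks and (b) the share of all eligible cases, as found under the 182-day window, that the candidate retains. Define the optimum as the shortest look-back that keeps a pre-set high share of eligible cases. The level is for the sponsor to choose and should be fixed before the table is seen; 95% is an example. Showing (b) separately for vaccinations before pregnancy start would be useful, since an overall figure can hide a larger loss there.

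The cost is a change of wording and one further column from charts already to be reviewed. The chosen window will carry some discards, which the present wording seeks to minimise.
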